## 2.3 Randomization and Blinding

The study was randomized, but it was open label upon individual subject treatment group assignment.

### 2.3.1 Methods of Randomization

Cohorts 1 and 2 (n=12 and n=24 but truncated to n=11, respectively) were randomized separately to receive a single dose of COVID-HIG via IM, SC, or IV. Randomization was stratified by SARS-CoV-2 detectable antibody status ( $\geq 15$ , but  $\leq 80$  AU/mL on the Diasorin LIAISON SARS-CoV-2 S1/S2 IgG antibody assay) and undetectable antibody ( $< 15$  AU/mL) at screening; subjects with antibody  $> 80$  AU/mL were excluded from the study as screen failures. The randomization was blocked in groups of 3 subjects assigned one each to the 3 treatment groups, so while the overall numbers of antibody-positive and antibody-negative subjects were not prespecified for Cohort 1, the site was instructed to complete all four blocks of three subjects. After enrollment of Cohort 1 was finished, enrollment caps were to be set for Cohort 2 to control the overall numbers of antibody-positive and antibody-negative subjects enrolled to be approximately equal; 18 or 21 antibody-positive subjects of 36 total subjects was permissible. Once randomized, subjects were not replaced even if not dosed.

Anti-SARS-CoV-2 Immunoglobulin Intravenous (Human) (NP-028), abbreviated as COVID-HIG  
EBS-CVH-006 Statistical Analysis Plan

**Table 2 Schedule of Events**

	In-clinic	In-clinic overnight stay			In-clinic or home healthcare/telemedicine visit										Withdrawal Visit (WV)	Unscheduled
		Screening	Day -1	Day 1	Day 2	Day 3*	Day 4	Day 6*	Day 8	Day 15	Day 29	Day 43	Day 57			
Visit Window (days in relation to Day 1)	≤14 days	≤1 day		1±0.5	2±0.5	3±0.5	5±0.5	7±1	14±2	28±2	42±3	56±3				
Informed consent	X															
Eligibility	X	X 														
Demography (age, sex, race/ethnicity, height, body weight, BMI)	X															
Medical history & ongoing medications 	X	X														
Complete physical exam 	X															
Targeted physical exam		X 	X 	X 	X 	X 	X 	X 	X 	X 	X 	X 	X 	X 		
Randomization and dosing			X													
Vital signs 	X		X 	X	X 	X	X 									
Safety laboratory tests 	X			X	X 	X	X 									
Urinalysis 	X			X	X 	X	X 									
Serum pregnancy test, if WOCBP	X 														X 	
Urine pregnancy test, if WOCBP		X 														
FSH test, if postmenopausal female	X 															
Urine drug screen	X															
Alcohol breath test		X														
Viral markers (HBV surface Ag, HCV Ab, HIV 1/2 Ab) 	X												X	X		
NP sample for SARS-CoV-2 RT-PCR	X	X		X 	X 	X 	X 	X	X	X	X	X	X	X 	X 	
Rapid SARS-CoV-2 IgM/IgG test	X	X														
Rapid SARS-CoV-2 antigen test	X															
Serum sample for Diasorin LIAISON SARS-CoV-2 S1/S2 IgG assay	X															
Serum sample for SARS-CoV-2 Ab PK		X	X 	X	X	X	X	X	X	X	X	X	X	X		
AEs & concomitant medications	X	X	X	X	X	X	X	X	X	X	X	X	X	X	X	
Confirm use of contraceptives (if appropriate)	X	X	X	X	X	X	X	X	X	X	X	X	X	X	X	

Anti-SARS-CoV-2 Immunoglobulin Intravenous (Human) (NP-028), abbreviated as COVID-HIG  
EBS-CVH-006 Statistical Analysis Plan

Counselling on precautions to prevent SARS-CoV-2 infection and assess COVID-19 symptoms/exposure. 	X	X 		X 	X	X	X	X	X	X	X	X	X	X
---	---	-----------------	--	-----------------	---	---	---	---	---	---	---	---	---	---

\* Visits on Day 3 and Day 6 are not necessary for the IV arm (Arm 3)

 Medical history information will be collected from participants at the Screening Visit and confirmed (and updated, if required) at the Day -1 Visit and will include (but not be limited to) demographic information (date of birth, race, ethnicity, and sex of participant), current and past medical conditions, prior and concomitant medications.

 Review and confirm eligibility.

 A complete physical examination will be performed on participants during the Screening Visit. The examination should include, general appearance, eyes-ears-nose-throat, head-neck, lungs-chest, heart, abdomen, musculoskeletal, lymph nodes, skin, extremities, and neurological assessment. A targeted physical exam may be performed on participants at additional time points if indicated by AE or SAE reporting.

 Vital signs collected from participants will include blood pressure, heart rate, SpO2 (pulse oximetry), respiratory rate, and temperature. Vital signs must be taken after  $\geq 10$  minutes resting. Vital signs can be repeated twice if grade 3 or higher to verify the severity. Body weight, height for BMI calculations will be obtained at Screening Visit.

 Collect resting vital signs within 2 hours prior to dosing and at  $30 \pm 5$  mins and 1 hour  $\pm 10$  mins postdosing (from end of infusion/injection).

 Clinical chemistry assessments will include the Chem 7 panel [Na+, K+, Cl, HCO3, BUN, creatinine, glucose], total and direct bilirubin, ALT, AST, LDH, and CBC with differential.

 Urinalysis will include appearance and color, specific gravity, protein, glucose, pH, occult blood. Initial analysis will be by dipstick, with further testing and microscopic examination only if clinically indicated.

 Serum pregnancy tests will be performed at Screening for all females of childbearing potential. Urine pregnancy tests will be performed on Day -1 visit for all females of childbearing potential. Pregnancy tests are not required for female participants who are postmenopausal  $\geq 12$  months, or surgically sterilized. Follicle stimulating hormone levels will be evaluated for females who are postmenopausal for  $\geq 12$  months.

 Viral markers include: HBsAg, HCV antibody, HIV-1/2. HCV RNA will be performed in HCV antibody positive individuals only.

 Collect serum PK samples at pre-dose (within 2 hrs prior to dosing) and postdose (from end of infusion/injection) at 1 hr  $\pm 10$ min, 2 hrs  $\pm 15$ min, 4 hrs  $\pm 15$ min, and 8 hrs  $\pm 30$ min, and 12 hrs  $\pm 30$ min.

 If COVID-19 symptoms are present or high-risk exposure has occurred based on investigator's discretion, an NP sample can be collected for SARS-CoV-2 RT-PCR. If participant tests positive for SARS-CoV-2 prior to dosing, they are no longer eligible to be enrolled.

 At Day -1 visit, participants will be assessed for COVID-19 symptoms/exposure only. At Day 2 visit, prior to discharge, participants will be counselled on precautions/measures to prevent SARS-CoV-2 infection.

 Assessment to be performed only if clinically indicated (as per investigator's discretion during in-clinic, home healthcare or telemedicine follow-up).

Anti-SARS-CoV-2 Immunoglobulin Intravenous (Human) (NP-028), abbreviated as COVID-HIG  
EBS-CVH-006 Statistical Analysis Plan

Separate blinded randomization lists were created for antibody-positive and antibody-negative subjects, and randomization assignment was performed by the Randomization and Trial Supply Management (RTSM) system vendor in the order the subjects were randomized in the applicable stratum. When the treatment group was assigned to a subject, then that subject's assignment was unblinded to the Sponsor and all study staff for dosing. The blinded randomization schedules were not available to the site prospectively.

### **2.3.2 Randomization Errors**

A *misrandomization* is defined as a subject receiving a study treatment other than the one assigned by randomization.

A *stratification error* occurs when a subject is randomized based on incorrect stratification information at baseline or if a subject is mistakenly put into the wrong block. In either case, the subject uses up one position in the assigned block and randomization continues.

Both misrandomizations and stratification errors are reported as protocol deviations (PD).

### **2.3.3 Blinding and Unblinding**

The RTSM system vendor created the blinded randomization lists and administered the randomization assignments. All study staff were blinded to the randomization schedule until each subject was assigned a treatment group in the order randomized, then that subject's assignment was unblinded to the study staff for dosing. The study proceeded as an open-label study after randomization.

## **3 STUDY ENDPOINTS**

### **3.1 Pharmacokinetic Endpoints**

#### **3.1.1 Primary Pharmacokinetic Endpoints**

The following primary PK endpoints, based on PK sample test results of an immunobinding IgG assay and a pseudovirus neutralization assay, were to be evaluated in healthy adults. However, Protocol Amendment 3.0 removed the pseudovirus neutralization assay PK analysis due to low sensitivity of this assay, so only the immunobinding IgG assay PK endpoints were analyzed:

- $AUC_{0-\text{inf}}$ :  $AUC_{0-\text{last}}$  plus the additional area extrapolated to infinity after dosing
- $AUC_{0-\text{last}}$ : area under the concentration-time curve from time 0 to the last quantifiable concentration after dosing
- $C_{\text{max}}$ : maximum observed concentration after dosing
- $T_{\text{max}}$ : time at which  $C_{\text{max}}$  occurs after dosing
- $C_{28d}$ : observed or estimated concentration at Day 29 (28 days after dosing)

Anti-SARS-CoV-2 Immunoglobulin Intravenous (Human) (NP-028), abbreviated as COVID-HIG  
EBS-CVH-006 Statistical Analysis Plan

### **3.1.2 Secondary Pharmacokinetic Endpoints**

The following additional COVID-HIG PK endpoints, based on PK sample test results by an immunobinding IgG assay and a pseudovirus neutralization assay, were to be calculated when data permit. However, Protocol Amendment 3.0 removed the pseudovirus neutralization assay PK analysis due to low sensitivity of this assay, so only the immunobinding IgG assay PK secondary endpoints were analyzed when data permitted:

- AUC0-inf ratios (bioavailability) will be compared between routes for comparable dose levels (COVID-HIG SC to IV; IM to IV; and SC to IM)
- AUC0-14d after dosing
- AUC0-28d after dosing
- $\lambda_z$ : terminal elimination rate constant after dosing
- $T_{1/2}$ : apparent terminal elimination half-life after dosing
- CL: systemic clearance after dosing
- $V_z$ : volume of distribution after dosing

### **3.2 Exploratory Efficacy Endpoint**

Descriptive analyses of COVID-19 disease severity were assessed by an Ordinal Outcome Scale (see protocol Appendix II).

### **3.3 Safety Endpoints**

The following safety endpoints were evaluated:

- AEs within 72 hours post-dosing
- AEs and SAEs in healthy adults up to 56 days post-administration of a single COVID-HIG dose (changed from to 84 days post-administration in Protocol Amendment 3.0)

## **4 POWER AND SAMPLE SIZE CONSIDERATIONS**

There was no formal sample size calculation for this Phase 1 study. However, based on previous experience with hyperimmune globulin products manufactured by Emergent in Phase 1 clinical studies with healthy adults, Emergent deemed the number of participants planned to receive study treatments in the study (N=36; n=12 per each treatment arm planned and N=23; n=7-8 per each treatment arm after study truncation in Protocol Amendment 3.0) sufficient to descriptively assess COVID-HIG safety and PK of a single dose in healthy adults.

Anti-SARS-CoV-2 Immunoglobulin Intravenous (Human) (NP-028), abbreviated as COVID-HIG  
EBS-CVH-006 Statistical Analysis Plan

## 5 DATA CONSIDERATIONS

### 5.1 Protocol Deviations

PDs were identified through monitoring and through programmatic and data checks. All identified subject-level PDs were entered in the sponsor's Clinical Trial Management System (CTMS) and classified by category, subcategory, and type (important/not important) per the Protocol Deviations Management Plan (PDMP) by the Sponsor study team. Important PDs (ICH E3, 1996) were defined as those that may significantly affect a subject's rights, safety, or well-being or impact the completeness, accuracy, and/or reliability of the study data.

PD categories for this study included: subject eligibility, investigational product administration, study visits, study procedures, laboratory assessments, safety monitoring, and noncompliance.

#### 5.1.1 Important Protocol Deviations

Examples of important PDs include:

- Subjects who did not sign informed consent prior to study-specific procedures, including reconsent
- Subjects who were randomized but did not meet study eligibility criteria
- Subjects who received no investigational product, received the wrong treatment route or dose level, or had investigational product (IP) administered via an incorrect method
- Subjects who received a prohibited concomitant medication, such as but not limited to COVID-19 vaccination
- Subjects who missed visits or assessments pertaining to key study endpoints (i.e., PK sample collection)
- Other deviations from key study procedures such as incomplete safety follow-up for an SAE or pregnancy, etc.

Subjects who contracted COVID-19, making subsequent PK samples ineligible for analysis, were recorded as AEs and not PDs.

#### 5.1.2 Reporting of Protocol Deviations

The number of subjects with important PDs is summarized by PD category and treatment group. PD listings by subject are provided in the clinical study report (CSR).

### 5.2 Analysis Populations

Analysis is based on the following study populations:

Intent-to-Treat (ITT) Population: All randomized participants. Subjects are analyzed according to the treatment arm to which they were randomized.

Anti-SARS-CoV-2 Immunoglobulin Intravenous (Human) (NP-028), abbreviated as COVID-HIG  
EBS-CVH-006 Statistical Analysis Plan

**Safety Population:** All participants who were randomized and received any amount of COVID-HIG IM, COVID-HIG SC, or COVID-HIG IV. Subjects are analyzed according to the treatment arm received. This population is used for all safety analysis.

**PK Population:** All participants who were randomized and received COVID-HIG IM, COVID-HIG SC, or COVID-HIG IV according to the protocol, have adequate data for calculation of PK parameters, and have no important PDs that would affect PK assessment (i.e., COVID-19 vaccination or COVID-19 infection, either of which result in all PK time points post-vaccination date or post-test date excluded from PK analysis). Subjects are analyzed according to the treatment arm received. This population is used for all PK analysis.

**SARS-CoV-2 Positive Population:** Any randomized participant (whether or not dosed with COVID-HIG) who tested positive for SARS-CoV-2 during the study period. Subjects are analyzed according to the treatment arm to which they were randomized. This population is used for the COVID-19 symptom severity exploratory endpoint.

### **5.3 Analysis Groups**

Tables are displayed by treatment arm (IM, SC, IV) columns and overall, for selected tables only. Data for subjects in Cohorts 1 and 2 are combined for all analyses.

### **5.4 Analysis Time Points**

For PK analyses, SARS-CoV-2 antibody levels were assessed at screening, Day 1 (baseline) pre-dose and postdose (from end of infusion/injection) at 1 hr  $\pm$ 10 min, 2 hr  $\pm$ 15 min, 4 hr  $\pm$ 15 min, 8 hr  $\pm$ 30 min, and 12 hr  $\pm$ 30 min, Day 2  $\pm$ 0.5 day, Day 3  $\pm$ 0.5 day (excluding IV arm), Day 4  $\pm$ 0.5 day, Day 6  $\pm$ 0.5 day (excluding IV arm), Day 8  $\pm$ 1 day, Day 15  $\pm$ 2 day, Day 29  $\pm$ 2 day, Day 43  $\pm$ 3 day, and Day 57  $\pm$ 3 day. Since PK analyses use actual and not nominal day and time, out of window data entered as study visit data (i.e., not an unscheduled visit) are included in the analysis. In general, all available data are included in the summaries according to the analysis set defined for a subject's inclusion.

Data collected at unscheduled visits are not presented in the by-visit summary analyses but are included in the summary tables by maximum toxicity grade or abnormality when applicable, and in data listings.

### **5.5 Definition of Baseline**

For all analyses, the baseline value for each measure is defined as the last non-missing value prior to IP dosing.

### **5.6 Multiple Records in an Analysis Window**

For clinical laboratory data, vital signs, and physical examinations, if multiple valid non-missing observations exist in an analysis window for a specific visit, a single value is chosen in the by-visit summary analyses based on the following rules:

Anti-SARS-CoV-2 Immunoglobulin Intravenous (Human) (NP-028), abbreviated as COVID-HIG  
EBS-CVH-006 Statistical Analysis Plan

- if the analysis values are numeric and the toxicity grades are available, the record with the highest toxicity grade is selected;
- if the analysis values are numeric and the toxicity grades are identical or not available, the last (newest) value is used;
- if the analysis values are categorical, the most conservative value is selected (e.g., abnormal will be selected over normal).

## 5.7 Coding Dictionaries

Medical history and adverse events were coded to system organ class (SOC) and preferred term (PT), based on the Medical Dictionary for Regulatory Activities (MedDRA) dictionary version 23.1.

Prior and concomitant medications and procedures were coded according to the World Health Organization's (WHO) WHO-Drug Global Dictionary version Sep2021 to Anatomical Therapeutic Chemical (ATC) classification and preferred drug name.

## 5.8 Toxicity and Severity Grading

AE severity (Grade 1 = Mild, Grade 2 = Moderate, Grade 3 = Severe, Grade 4 = Potentially Life-threatening) was graded according to the Division of Acquired Immunodeficiency Syndrome (DAIDS) Severity Grading Scale per protocol [Appendix I I](#) (DAIDS, 2017). Note that AEs that result in death are classified as Grade 5.

Severity of abnormal vital signs was assessed by the Investigator or designee using the criteria in [11Appendix I](#). Clinical laboratory results were graded by the Investigator or designee. For symptoms not appearing on the grading scale, the grading for generic “illness or clinical AE” were used (see protocol Table 5). Grade 0 was used to represent “normal” or “symptom not present.” Values within the normal range as well as out of range laboratory values not meeting criteria for severity of at least Grade 1 are considered Grade 0.

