3.3 Measures Taken to Minimize/Avoid Bias

3.3.1 Masking/Blinding Procedures

As this is an open label study, no masking/blinding procedures are necessary.

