9.4.3.3 Clinical Laboratory Test Results

Hematology and clinical chemistry laboratory test results and change from baseline to Day 2 and Day 4 will be summarized by time point and administration route for the safety population. The clinical significance of any abnormality will be assessed by the investigator. Abnormal laboratory results will be graded with severity grade 1 to 4 (grade 1=mild, through grade 4=potentially life-threatening) according to the DAIDS Table for Grading the Severity of Adult and Pediatric Adverse Events ([Appendix I](#)). Values within the normal range as well as out of range laboratory values not meeting criteria for severity of at least grade 1 will be considered grade 0. Shift tables of laboratory abnormalities (Low, Normal, High) and/or severity grade (0,

Anti-SARS-CoV-2 Immunoglobulin Intravenous (Human) (NP-028), abbreviated as COVID-HIG
EBS-CVH-006, Version 3.0, 18 Feb 2022

1-2, ≥ 3) will be provided for selected laboratory parameters summarized by time point and administration route for the safety population.

Results for urinalysis, pregnancy tests, and viral markers will be listed by participant.

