## **9.4 Clinical Laboratory Tests**

### **9.4.1 Safety Laboratory Tests**

Clinical laboratory analytes included Na+, K+, Cl-, HCO3-, BUN, creatinine, glucose, total and direct bilirubin, ALT, AST, LDH, and CBC with differential. Urinalysis parameters included appearance, bilirubin, color, glucose, ketones, leukocyte esterase, nitrite, occult blood, pH, protein, specific gravity, and urobilogen. Clinical laboratory tests were required at Day 2 and 4; at other visits, tests were done as clinically indicated only. Clinical laboratory test results were assigned a toxicity grade by the investigator as described in Section 5.8.

Safety laboratory measurements are summarized as follows for the Safety population:

- Observed values and changes from baseline of continuous laboratory variables (hematology and serum chemistry) are summarized using descriptive statistics by study visit and treatment arm.
- Shifts from baseline in hematology and serum chemistry analyte values according to normal reference ranges (reported as 'Low,' 'Normal,' and 'High') or toxicity grades (Grade 0, 1-4) are summarized (number and percentages) by study visit and treatment arm.

Anti-SARS-CoV-2 Immunoglobulin Intravenous (Human) (NP-028), abbreviated as COVID-HIG  
EBS-CVH-006 Statistical Analysis Plan

- Frequency and percentage of subjects with the highest toxicity grade of abnormal hematology and serum chemistry laboratory values at any time on study are summarized by study visit and treatment arm. In this analysis, analytes with toxicity criteria for both increases and decreases are presented separately for each direction (e.g., sodium increased and sodium decreased).
- Urinalysis data are listed only.

All laboratory records (including local laboratory measurements if applicable) are provided in the subject data listings, with applicable toxicity grades or abnormal flags displayed.

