### **9.5 Vital Signs, Physical Findings, and Other Variables Related to Safety**

#### **9.5.1 Vital Signs**

Vital signs parameters included blood pressure, heart rate, SpO2 (pulse oximetry), respiratory rate, and temperature. Vital signs were assessed at screening, on Day 1 (baseline) at pre-dose and 30 min and 1 hour after the end of dosing, and on Days 2, 3 (except IV arm), 4, 6 (except IV arm), 8, 15, 29, 43, and 57. Vital sign test results were assigned a toxicity grade by the investigator using the criteria in [11 Appendix I](#) as described in Section [5.8](#).

Vital sign data are summarized as follows for the Safety population:

- Shift from baseline in toxicity grade (Grade 0-4) are summarized (number and percentages) by study visit and treatment arm.

All vital sign records are provided in the subject data listings.

Anti-SARS-CoV-2 Immunoglobulin Intravenous (Human) (NP-028), abbreviated as COVID-HIG  
EBS-CVH-006 Statistical Analysis Plan

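### Safety tables use laboratory and vital-sign grades assigned by unmasked site staff, with no stated derivation from or check against the recorded values, though most vital-sign grades have numeric cut-offs

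*SAP*

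**What the plan says.** SAP 5.8 names the grader for both kinds of data. For laboratory results: "Clinical laboratory results were graded by the Investigator or designee". For vital signs: "Severity of abnormal vital signs was assessed by the Investigator or designee using the criteria in" SAP Appendix I, which carries the same table as Protocol Appendix III. The analysis sections repeat this. SAP 9.4.1 states "Clinical laboratory test results were assigned a toxicity grade by the investigator as described in Section 5.8", and SAP 9.5.1 states "Vital sign test results were assigned a toxicity grade by the investigator using the criteria in" that appendix.

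The graders know the route. Protocol 3.3.1: "As this is an open label study, no masking/blinding procedures are necessary". SAP 2.3.3: "The study proceeded as an open-label study after randomization".

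The grades are then used in three places:

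- **Vital signs (SAP 9.5.1).** The only table is the shift in grade from baseline. The recorded values appear in listings.
- **Laboratory (SAP 9.4.1).** One table gives the highest grade. Shift tables use either reference-range categories or grades. Recorded values and changes from baseline are also summarised as continuous variables.
- **Choice of record (SAP 5.6).** If several numeric results fall in one visit window and grades are available, "the record with the highest toxicity grade is selected". If the grades are identical or not available, the latest value is used.

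Protocol 9.4.3.3 says "The clinical significance of any abnormality will be assessed by the investigator" and that abnormal results are graded by the DAIDS table, without naming a grader. Protocol 9.4.3.4 does the same for vital signs, by Appendix III.

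**The concern.** A grade with a fixed numeric limit can be computed exactly from a value already in the database. Analysing a grade supplied by the site instead lets in transcription or application error and differences between the two sites. Where the criteria leave room, it also lets in knowledge of the route. Safety of the IM and SC routes is a primary objective, and the tables are read by route.

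Exposure is greatest for vital signs. Protocol 9.4.3.4 plans a summary of the values and their change from baseline, with shift tables optional; SAP 9.5.1 keeps only the grade shift. No summary of the recorded numbers therefore stands beside the table to offset or reveal a wrong grade.

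**Working it through.** No sample-size, power or alpha figure bears on this point. The check is a count of the grading table, two worked readings of the rules, and the weight of one participant.

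**1. How much of the vital-sign scale is numeric (SAP Appendix I)?**

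- Cells: 8 parameters × 4 grades = 32.
- Grades 1 to 3 are numeric for all parameters: 8 × 3 = 24.
- Temperature Grade 4 is numeric: 1.
- Grade 4 rests only on an event (ER visit, hospitalization or intubation) for tachycardia, bradycardia, systolic hypertension, diastolic hypertension, systolic hypotension and respiratory rate: 6.
- SpO2 Grade 4 is numeric or event: 1.
- Check: 24 + 1 + 6 + 1 = 32. Purely numeric: 25/32 = 78%.

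**2. Where can two sites differ on the same reading?** SAP 5.8 has the site grade abnormal vital signs and uses Grade 0 for normal ones. Protocol 9.4.3.4 likewise sets values in the normal range to Grade 0. Neither document defines a normal range for vital signs. In Appendix I a respiratory rate of 17 to 20 is Grade 1. A grader who regards that rate as normal could leave it at Grade 0, and nothing in either document settles which entry is right for the table.

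**3. What does the record rule do?** Appendix I allows vital signs to be repeated when the grade is 3 or higher, which is a setting where grades may differ. Take a systolic pressure of 156 (Grade 3, above 155) and a repeat of 148 (Grade 1, range 141 to 150).

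- Both grades entered: SAP 5.6 selects 156, and Grade 3 enters the shift table.
- First grade left blank, and the rule read as grades not available: the latest value is selected, 148, and Grade 1 enters.
- Grades derived from the values: 156 is selected in either case.

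SAP 5.6 does not say what happens when only one of two grades is present. The rule matters only when repeats fall in one window and their grades differ or are missing.

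**4. Weight of one participant.** SAP 4 gives 23 participants, 7 or 8 per arm. 1/8 = 12.5%; 1/7 = 14.3%.

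**5. Laboratory grades.** The DAIDS cut-offs are not reproduced in the documents, so the number of analytes with numeric criteria cannot be counted here. Protocol 8.2.2 sends analytes without DAIDS criteria to a clinical-AE scale applied by the PI or designee. That scale cannot be computed from a number.

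**The case against.** The strongest reply is that the SAP does what the protocol intends. Protocol 8.1.8 has the investigator or sub-investigator grade AEs, laboratory abnormalities included, by the DAIDS table. Protocol 8.2.2 gives the PI or designee the grading of analytes without criteria. Repeating vital signs at Grade 3 or higher presupposes a grade at the site. A reader might infer from Protocol 9.4.3.3 and 9.4.3.4 that the investigator is confined to clinical significance and that the SAP departs from the protocol. The documents do not support that: those sections leave the grader unnamed, and the others place grading with the site.

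Nor do the documents say that grades are entered by hand. They name the grader, not the mechanism, and SAP 1 puts some derivation detail in table shells that are not part of these documents.

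The reply is also right about scale. Fixed cut-offs leave little room for expectation about route. Laboratory data have continuous summaries, and their shifts may use reference ranges. Records are listed, and monitors verify eCRF entries against source (Protocol 11.1). SAP 5.4 keeps unscheduled-visit data out of by-visit summaries, which limits how often SAP 5.6 has a choice to make for laboratory repeats.

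All of this limits the harm. It does not supply a stated check, and it leaves a reader to regrade the listings before relying on the vital-sign table.

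**Conclusion.** The point holds as a modest one. The SAP tabulates grades assigned by unmasked site staff and states no derivation or check, although most vital-sign grades could be computed. The known size is the weight of one participant: 12.5 or 14.3 percentage points in an arm.

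Two stronger readings go beyond the documents:

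- **A count of wrong grades.** One might multiply scheduled measurements (6 × 5 × 23 = 690 for vital signs; 21 × 3 × 23 = 1,449 for laboratory values) by an error rate. The protocol and SAP have abnormal values graded and set the rest to Grade 0 by rule, so these are not counts of site-assigned grades. No error rate is given either.
- **Damage to the primary safety endpoints.** The endpoints in Protocol 3.2.3.1 are AEs and SAEs, not grade shifts. There is an indirect link, since Protocol 8.2.2 makes a laboratory value of Grade 3 or higher on retest or repeat an AE. Nothing in the documents shows that any such value was misgraded.

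The conclusion assumes that the table shells contain no programmed grading, and that recorded values are in the analysis database, as the planned listings imply.

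**What to change.** Amend SAP 5.6, 5.8, 9.4.1 and 9.5.1 as follows, for analysis only:

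- Derive by program, from the recorded value, every grade with a numeric criterion. For vital signs these are Appendix I Grades 1 to 3 and the numeric Grade 4 limits (temperature, and the numeric part of SpO2). For laboratory analytes with numeric criteria, use DAIDS version 2.1.
- State that the Appendix I cut-offs take precedence over an undefined normal range when Grade 0 is assigned.
- Use the derived grades to choose between records in SAP 5.6 and in the shift and maximum-grade tables.
- Keep the investigator's grade for event-based criteria and for analytes without DAIDS criteria.
- List discrepancies between derived and site-assigned grades.

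The SAP is written largely in the past tense, so site grading appears to be complete. This is a change at the analysis stage, with no change in conduct and no new data. The cost is SAP wording, modest programming, and a short list of discrepancies with eCRF grades to explain in the study report.
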